### **9.7.Prohibited drugs**

Concomitant administration of interleukin-6 receptor inhibitors and immunomodulatory drugs is not permitted.

Concomitant use of chloroquine and derivatives is not permitted.

Patients may receive other pharmacological treatments for COVID-19 at the discretion of the investigator after 24 hours from the administration of the last dose of plitidepsin.

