  - 9 The first time the patient tested positive for COVID-19 will be included as well. The test will be repeated in the 48 hours prior to administration of plitidepsin and on days 4, 7, 15 and 31, if negative detection does not occur before then. Qualitative PCR shall be obtained on nasopharyngeal exudate (preferably) or a sample from the lower respiratory tract.
  - 10 A chest X-ray will be performed at baseline and subsequently based on clinical discretion.
  - 11 Only fertile women.
  - 12 Patients may receive other pharmacological treatments for COVID-19 at the discretion of the investigator 24 hours after administration of the last dose of plitidepsin.
  - 13 Adverse events (serious and non-serious) will be recorded from signing of the informed consent up to 28 days after administration of the last dose of plitidepsin.
  - 14 A safety visit will be made 28 days (+3 days) after the last dose of plitidepsin.
  - 15 The viral load should be determined in a sample obtained from nasopharyngeal exudate (preferably) or a sample from the lower respiratory tract.

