1 INTRODUCTION

This statistical analysis plan describes the protocol-defined final analysis that will be performed in the APLICOV-PC study (APL-D-002-20).

Given the characteristics of the study, continuous safety analyses up to 12 days after the last administration of plitidepsin of each patient evaluable for safety in each of the arms of each group of 9 patients are planned to be performed. These analyses will be performed for every 3 patients included in each arm of each cohort, before continuing with the inclusion of more patients in the study. After the recruitment of the 27 initially planned patients, an additional 18 patients will be included (6 at each dose level) to expand the collection of safety information of the different doses and to increase the efficacy data.

This SAP version applies to the final statistical analysis that will be the basis of the clinical study report and it will be made on the total population of 45 patients. These analyses will be descriptive and the data will be presented by treatment arm.

Abbreviations:

Abbreviation	Term
AE	Adverse Event
ALT	Alanine Aminotransferase
AST	Aspartate Aminotransferase
BPM	Breaths per minute or Beats per minute
CPK	Creatine Phosphokinase
DBP	Diastolic blood pressure
eCRF	Electronic Case Report Form
ECG	Electrocardiogram
GGT	Gamma-glutamyltransferase
ICU	Intensive care unit
IL-6	Interleukin 6
LDH	Lactate dehydrogenase
SAE	Serious Adverse Event
SBP	Systolic blood pressure

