7.4 Concomitant medication

- Description of the concomitant medication: number of patients and percentage of some concomitant medication will be presented by dose and ATC levels.

The following variables will be analyzed per visit:

- Requirement of another specific treatment for COVID-19 (Yes; No).
- Support treatment requirement (Yes; No). For those patients who have received supportive treatment, the treatment and description in the database (discrete) and the treatment scheme taking into account the active principle of the medication (discrete) will be analyzed. The number and percentage of patients that require each of the schemes will be indicated and a detailed list of patients will be provided.
- Duration of corticosteroids treatment.
- Duration of antibiotic treatment

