8.1 Efficacy evaluation

The following tests will be performed to evaluate the efficacy of the treatment:

a) Viral load evolution:

For the analysis of the evolution of the viral load, the number and percentage of patients from who a sample has been collected will be indicated to determine the viral load at baseline and at visit 4, 7, 15 and 31 describing the results in those patients (number of RNA copies detected and log of the number of copies). The result will be given to three decimal places.

The graphs of the evolution of the viral load (mean and median) of the patients from the baseline to the last visit will be presented. These graphs will be shown by separate for each dose level, by FDA baseline classification and Oxygen support or not on day 1.

In addition, the following variables will be analyzed:

- The number and percentage of patients who viral load result is maintained, decreased or increased with respect to the previous visit on days 4, 7, 15 and 31 will be presented.
- Negative detection (global and by dose level):
- The number and percentage of patients with negative or undetectable viral load on days 4,7,15 and 31.
- The number and percentage of patients with negative or undetectable viral load on days 4,7,15 and 31 in the subgroups of low, medium and high initial viral load.
- Time to negative detection (viral load 0 or undetectable) in overall patients from date of PCR at baseline.
- Time to negative detection (viral load 0 or undetectable) based on baseline viral load (high (>7 copies/mL) / medium [4-7 copies/mL] / low (<4 copies/mL)) and other baseline characteristics (sex, age, race, ...) will be explored.
- Time to negative detection based on corticosteroid treatment (<10 days vs > 10 days)
- Viral load (high, medium, low) will be correlated with study outcome variables such as need for oxygen therapy, admission to ICU (Yes / No), NIMV, IMV, days of hospitalization, death (Yes / No).

- Determine the relationship between the number of days with symptoms and having a higher or lower viral load.
- Determine the relationship between viral load and the baseline situation of the patient, mild-moderate-severe, oxygen need / no need.
- The relationship between viral load and different inflammatory parameters (LDH, ferritin, C-reactive protein, D-dimer and lymphocytes) will be graphically analyzed.
- The mean change in viral load log₁₀ RNA copies/mL from baseline to day 4, 7, 31 will be analyzed in:
 - All patients

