High >7				
Total				

Table 12.1.11 Time to negative detection

Time to negative detection	Time to negative detection			p-value(**)
	N	Median	Range	
Viral load at baseline				
Low <4				
Medium [4-7]				
High >7				
Dose				
1.5 mg				
2.0 mg				
2.5 mg				
Age				
< 65 y.o.				
>=65 y.o.				
Sex				
Female				
Male				
Race				
White				
Other				
... (*)				

(*) FDA risk groups (Mild, moderate, severe), Oxygen need (Yes/No), Chronic lung disease (Yes/No), Corticosteroids (Yes/No), Other antiviral treatment for COVID-19 (Yes/No). Further variables could be added upon request

(**) Kruskal-Wallis

Table 12.1.12 Time to negative detection by corticosteroid duration

Time to negative detection	Corticosteroid duration		p-value*
	< 10 days	>= 10 days	
Dose			
1.5 mg			
2.0 mg			
2.5 mg			
Total			

(**) Kruskal-Wallis

Table 12.1.13 Oxygen therapy

Number of patients (%)	Dose Cohort							
	1.5 mg N=X		2.0 mg N=X		2.5 mg N=X		Total N=X	
	Oxygen therapy							
	Yes	No	Yes	No	Yes	No	Yes	No
Oxygen therapy at baseline								
Yes								
No								
Chronic Lung Disease								
Yes								
No								
Age								
< 65 y.o.								
>=65 y.o								
Gender								
Female								
Male								
Race								
White								
Other								
Viral load at baseline								
Low <4								
Medium [4-7]								
High >7								
FDA Risk groups								
Mild								
Moderate								
Severe								

Listing 12.1.14 Oxygen therapy evolution

Subject id	Dose	Visit	Date	Time	Oxygen therapy type	Flow

Table 12.1.15 Oxygen therapy onset day

Onset day	Dose Cohort							
	1.5 mg N=X		2.0 mg N=X		2.5 mg N=X		Total N=X	
From start of symptoms								
From first plitidepsin dose								
From corticosteroids use								

Table 12.1.16 Patients changing oxygen therapy

	Dose Cohort			
	1.5 mg N=X	2.0 mg N=X	2.5 mg N=X	Total N=X
From no Oxygen therapy to Oxygen therapy				
From low flow to high flow				
From high flow to low flow				

Table 12.1.17 Time in (ICU- Invasive M Ventilation – Non Invasive MV – in Hospital)

Time (days)	Dose Cohort			
	1.5 mg N=X	2.0 mg N=X	2.5 mg N=X	Total N=X
ICU				
Invasive mechanical ventilation				
Non Invasive mechanical ventilation				
Hospital*				

(*)From first infusion

Table 12.1.18 Reason for ICU discharge

Endpoint	Dose Cohort			
	1.5 mg N=X	2.0 mg N=X	2.5 mg N=X	Total N=X
Reason for ICU discharge, n (%)				
Taken back to the ward				
Death				

Table 12.1.19 ICU admission according to oxygen therapy or chronic lung disease

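### Splitting time to negative detection by total corticosteroid duration, with a p-value, can show a difference when steroids have no effect (minor)

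*SAP*

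**What the plan says.** SAP 8.1 a) lists, among the viral-load analyses, "Time to negative detection based on corticosteroid treatment (<10 days vs > 10 days"). The output is "Table 12.1.12 Time to negative detection by corticosteroid duration". It has a row for each dose and one for the total, columns for less than 10 days and for 10 days or more, and a p-value footnoted "Kruskal-Wallis".

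The time origin in SAP 8.1 a) is the baseline test: "Time to negative detection (viral load 0 or undetectable) in overall patients from date of PCR at baseline". The grouping variable appears in SAP 7.4 as "Duration of corticosteroids treatment", a quantity accumulated during follow-up. The item just before it in 8.1 a) splits the same endpoint by baseline viral load and other baseline characteristics; this one does not.

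Under Protocol section 10, PCR is repeated "on days 4, 7, 15 and 31, if negative detection does not occur before then". Protocol 9.7 allows other COVID-19 drugs "at the discretion of the investigator after 24 hours from the administration of the last dose of plitidepsin". The final analysis covers all patients: "it will be made on the total population of 45 patients".

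For this table the SAP gives no landmark, time-dependent covariate, severity adjustment, or rule for patients who die or never turn negative. SAP 4.6 foresees no imputation. SAP section 1 calls the analyses descriptive.

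**The concern.** Patients are sorted by something that happens after the clock starts and that may depend on the outcome. A patient who clears virus early, improves and comes off steroids falls into the short group; a sicker patient who stays positive may be kept on them and falls into the long group. Either route produces a difference in time to negative detection with no effect of steroids on the virus.

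The rank test treats the two columns as if they were fixed at baseline, and its p-value invites the reader to see an effect of course length. The efficacy data feed the joint dose evaluation by sponsor and agency, and this table is split by dose. A misleading p-value here would therefore sit beside results that do matter.

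**Working it through.** **No figure to reproduce.** The documents give no alpha, power or effect size for this comparison. The only count is the sample size: 27 + 18 = 45 in total and 9 + 6 = 15 per dose, which agree.

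**Timing.** A course starting on Day 1 reaches its tenth day on Day 10. If steroids count as other COVID-19 drugs under Protocol 9.7, the earliest start is 24 hours after the Day 3 dose, about Day 4, and the tenth day is 4 + 9 = Day 13. In both cases the Day 4 and Day 7 PCR results come before anyone can be known to belong to the long group.

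**Null simulation, assumption set A** (4,000 trials per case, N = 45, no steroid effect, Kruskal-Wallis at a nominal 5%). These assumptions are not in the documents:
- clearance time lognormal, median 11 days, log-SD 0.6, read on Days 4, 7, 15 and 31;
- planned course lognormal, median 10 or 14 days, log-SD 0.5, starting on Day 1 or Day 4;
- never-negative patients either excluded or ranked last.

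Ranges below cover the variants run.

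| Link between duration and clearance | Rejection rate |
|---|---|
| None | 4.6-5.2% |
| 25 / 50 / 75 / 100% stop at first negative PCR, planned median 10 days | 8-9 / 21 / 41-45 / 68-71% |
| 50 / 100% stop, planned median 14 days | 45-46 / 94-95% |
| Shared severity, correlation 0.3 / 0.5 / 0.7 | 25-33 / 64-74 / 95-98% |
| None, 10% or 20% deaths, never-negatives excluded | 4-5% |
| None, 10% or 20% deaths, never-negatives ranked last | 6-10%, short group looks slower |

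At correlation 0.5, with a Day 4 start and never-negatives excluded, mean time to negative is 14.1 days (short) against 20.2 days (long). Within one dose (n = 15), rejection is about 24-25% at correlation 0.5 or with 100% stopping.

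**Assumption set B.** Clearance median 10 days, log-SD 0.7; planned course uniform over 3-20 days; courses end at clearance itself. With 25 / 50 / 75 / 100% ending at clearance, rejection is 11-12 / 30-32 / 63-66 / 94-96% over repeated runs, and about 5% with no link. Starting courses around Day 4 takes the last figure to 99%.

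**Number of tests.** The layout allows four p-values (three doses and the total). Treated as independent, 1 - 0.95^4 = 0.185. The total contains the doses, so this is only approximate.

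**Does a landmark repair it?** A landmark at the tenth steroid day, among patients still positive, brings rejection back to 4-5% when steroids stop on a negative PCR. With shared severity it still rejects in about 14, 32 and 61% at correlations of 0.3, 0.5 and 0.7. A landmark removes the timing problem but not the confounding.

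**Definitions.** The text uses more than 10 days and the table uses 10 or more, so a course of exactly 10 days has no group in the text. Protocol 9.2 gives dexamethasone before each of three infusions, and the listing in SAP 9.6 excludes premedication; Table 12.1.12 is silent. If those days counted, 3 + 7 = 10, and a further 7-day course would move to the long column. The table also does not say whether non-users belong in the short column.

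**The case against.** The best defence has four parts.

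- **The grouping alone does not inflate the error.** A reader might infer that immortal-time bias is built in. The documents do not support that: a patient who goes on to a long course can turn negative on Day 4 or 7, so the event is not excluded while exposure accrues, and rejection stays near 5% when duration and clearance are unrelated. This stands.
- **The link is assumed.** Neither document says that steroids stop on a negative PCR, on recovery or at discharge. The simulations also give all 45 patients a course, whereas the SAP treats steroid use as yes/no and the efficacy population may be smaller. This stands for the size of the effect. The link is still plausible: the SAP lists high-dose corticosteroids as support treatment, relates the onset of oxygen and ventilation to steroid start, and plans to relate baseline severity to time to negative.
- **The direction is not fixed.** A reader might infer that the table will show longer steroids delaying clearance. Early deaths ranked as never negative push the other way. The efficacy population limits that case, since it requires at least two weeks of follow-up except for patients whose treatment stopped because the disease worsened.
- **Little hangs on it.** Nothing ties this table to the primary safety endpoint, the escalation rules or the handling of steroids in a later trial, and SAP 8.1 c) analyses time to negative PCR by Kaplan-Meier. This stands and sets the severity. It does not justify the p-value in an analysis described as descriptive.

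**Conclusion.** The point holds as a minor one. Table 12.1.12 compares time to negative detection across a post-baseline grouping open to reverse causation and to confounding by severity, and its p-value can mislead. With no steroid effect and N = 45, the false-positive rate is about 5% with no link, about 8-96% if 25-100% of courses end at clearance (99% in one variant), and about 25-98% if shared severity gives a correlation of 0.3-0.7. These figures illustrate what can happen. They rest on assumed clearance times, course lengths and links, and do not predict this trial's result. The cut-point mismatch and the undefined handling of premedication days and non-users are separate drafting gaps that need no assumption.

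**What to change.** Delete the p-value from Table 12.1.12, or drop the table. Label any remaining summary by duration as descriptive and not interpretable as a steroid effect.

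If a comparison is wanted, fit a Cox model for time to negative detection with corticosteroid use beyond premedication as a time-dependent covariate, adjusted for baseline FDA class, oxygen on Day 1 and baseline viral load. State that it addresses steroid use rather than course length, and that residual confounding remains. With three FDA classes this is 2 + 1 + 1 + 1 = 5 parameters on at most 45 patients, so it is exploratory. A Day 4 landmark is a weak substitute: if Protocol 9.7 covers steroids, few patients would be exposed by then, and it does not deal with severity.

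If the table is kept, use one cut-point in the text and the table, so that exactly 10 days has a group. State whether premedication days count and whether non-users enter the short column, and give a rule for patients who die or never turn negative.

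The cost is SAP wording and one exploratory table removed or re-programmed. The listings already carry medication start and end dates and corticosteroid onset day and duration, so no new data are needed.

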- Laboratory parameters, median (range) (WBC, x109/L, Platelet count, x109/L, Lymphocytes, x109/L, Serum creatinine, µmol/L, ALT x ULN, AST x ULN, LDH x ULN, CPK x ULN, GGT x ULN, C-reactive protein, Ferritin, D-dimer)
- log10 copies/mL viral load, median (range)

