Table 10.2.6 Clinical data (Signs and symptoms on admission) Baseline Characteristics

n (%)	Dose Cohort			
	1.5 mg N=X	2.0 mg N=X	2.5 mg N=X	Total N=X
*				

(*) Time from the beginning of the first symptom to hospital admission, Time from hospital admission to first dose of plitidepsin treatment, Fever, Dehydration, Cough, Sputum production, Hemoptysis, Runny nose, Earache, Crackles, Thoracic Pain, Muscular pain, Joint pain, Fatigue, Short of breathe, Intercostal retraction, Headache, Confusion, Convulsion, Abdominal pain, Vomiting\Nausea, Diarrhea, Conjunctivitis, Rash, Skin ulcer, Lymphadenopathy, Throat pain, Bleeding.

Table 10.2.7 Clinical data (Comorbidities) Baseline Characteristics (categorical variables)

n (%)	Dose Cohort			
	1.5 mg N=X	2.0 mg N=X	2.5 mg N=X	Total N=X
*				

(*)Chronic Cardiac pathologies, Arterial Hypertension, Chronic lung disease, Asthma, Diabetes with complications, Diabetes without complications, Chronic kidney disease, Rheumatic disorder, Moderate or severe liver disease, Mild liver disease, Dementia, Malnutrition, Chronic neurological disorder, Smoker, Malignant neoplasm, Chronic hematological disease, AIDS, obesity, Other risk factors, Other details.

Table 10.2.8 Vital signs at baseline Characteristics (categorical variables)

n (%)	Dose Cohort			
	1.5 mg N=X	2.0 mg N=X	2.5 mg N=X	Total N=X
*				

(*) Saturation, Oxygen therapy type, Chest X-Ray, Electrocardiogram, Result, FDA classification

Table 10.2.9 Six-point ordinal scale on Day 1

n (%)	Dose Cohort			
	1.5 mg N=X	2.0 mg N=X	2.5 mg N=X	Total N=X
1 Discharge (Alive)				
2 Hospital admission, not requiring supplemental oxygen				
...				

Table 10.2.10 Days with symptoms according to baseline viral load

	Viral Load at baseline (copies/mL)			p-value(*)
	Low <4	Medium [4-7]	High >7	
Days with symptoms				

(*) Kruskal-Wallis

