Day 1 to Day 7				
Day 8 to Day 15				
Day 16 to Day 31				
Patients requiring non-invasive mechanical ventilation at, n (%)				
Day 1 to Day 7				
Day 8 to Day 15				
Day 16 to Day 31				
Patients requiring oxygen therapy at, n (%)				
Day 1 to Day 7				
Day 15				
Day 31				
Patients requiring oxygen therapy (high flow) at, n (%)				
Day 7				
Day 15				
Day 31				
Patients requiring oxygen therapy (low flow) at, n (%)				
Day 7				
Day 15				
Day 31				

This table will be also performed by age (<65 vs. ≥65 year old) (12.1.5.1)

This table will be also performed by FDA classification (12.1.5.2)

Table 12.1.6 Summary of Protocol-Specified Efficacy Endpoints 95%CI

Dose Cohort															
1.5 mg				2 mg				2.5 mg				Total			
N	%	Exact CI Lower	Exact CI Upper	N	%	Exact CI Lower	Exact CI Upper	N	%	Exact CI Lower	Exact CI Upper	N	%	Exact CI Lower	Exact CI Upper

(*) Patients requiring Invasive Mechanical Ventilation; Patients requiring Non Invasive Mechanical Ventilation; Patients requiring ICU.

This table will be also performed by age (<65 vs. >=65 year old (12.1.6.1)
This table will be also performed by FDA classification (12.1.6.2)

Table 12.1.7 Viral load change from baseline and negative detection

Mean change in viral load from baseline to, log10 copies/mL	Dose Cohort			
	1.5 mg N=X	2.0 mg N=X	2.5 mg N=X	Total N=X
Day 4				
Day 7				
Day 15				
Day 31				
Mean time from baseline until undetectable viral load (days)*				

All patients (12.1.7.1), Mild & moderate patients (12.1.7.2), moderate patients (12.1.7.3), severe patients (12.1.7.4).

(*) From baseline PCR

Table 12.1.8 Viral load at baseline and study outcome variables

	Viral Load at baseline			
	Low <4	Medium [4-7]	High >7	p-value(*)
Oxygen therapy				
Yes				
No				
Oxygen therapy Low flow				
Yes				
No				
Oxygen therapy High flow				
Yes				
No				
ICU admission				
Yes				
No				
NIMV				
Yes				
No				
IMV				
Yes				
No				
Death				
Yes				
No				
Days of hospitalization				
FDA Risk groups				
Mild				
Moderate				
Severe				

(*)Fisher's exact test for categorical variables. Kruskal-Wallis test for continuous variables.

Table 12.1.9 Patients with negative detection

Number of patients (%)	Dose Cohort			
	1.5 mg N=X	2.0 mg N=X	2.5 mg N=X	Total N=X
Day 4				
Day 7				
Day 15				
Day 31				

Table 12.1.10 Patients with negative detection according to initial viral load

Number of patients (%)	Dose Cohort			
	1.5 mg N=X	2.0 mg N=X	2.5 mg N=X	Total N=X
Low <4				
Medium [4-7]				

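### Baseline viral load, held on a log10 scale, is tested against symptom days and outcomes only as three unordered classes, which gives up power in exploratory tables that could be had back at almost no cost

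*SAP*

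**What the plan says.** The SAP holds baseline viral load as a continuous quantity: section 5.2 summarises it as "log10 copies/mL viral load, median (range"), and section 8.1 a) asks for results to three decimals.

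For relations with other variables the scale is cut. Section 8.1 a) defines the classes for time to negative detection: "based on baseline viral load (high (>7 copies/mL) / medium [4-7 copies/mL] / low (<4 copies/mL"). It then says "Viral load (high, medium, low) will be correlated with study outcome variables such as need for oxygen therapy", and asks to "Determine the relationship between the number of days with symptoms and having a higher or lower viral load".

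The shells show the tests:

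- Section 10.2, "Table 10.2.10 Days with symptoms according to baseline viral load", has columns Low, Medium and High and a Kruskal-Wallis p-value.
- Table 12.1.8 crosses the same three classes with oxygen therapy (any, low flow, high flow), ICU, NIMV, IMV, death, days of hospitalization and FDA group. Its footnote reads "Fisher's exact test for categorical variables. Kruskal-Wallis test for continuous variables".
- Table 12.1.11 uses the same classes, with Kruskal-Wallis, for time to negative detection.

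No source or reason is given for 4 and 7. They are printed in copies/mL; I read them as log10 copies/mL throughout.

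**The concern.** Cutting a measured scale into three classes treats everyone within a class as alike. Kruskal-Wallis and Fisher's exact test then treat the classes as mere labels, so the ordering low, medium, high is not used either. Both steps lose information.

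These tables are where the SAP asks whether viral load goes with illness duration, severity and outcome. With 45 patients at most, a moderate association could easily give a non-significant p-value and be read as no relation. The result would also depend on where two unexplained cut points happen to fall in this sample.

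**Working it through.** **Inputs from the documents.** SAP section 1: the final analysis "it will be made on the total population of 45 patients". This is an upper limit, since the efficacy population is restricted and samples may be missing. Cuts at 4 and 7. Tests as in the table footnotes.

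**Inputs not in the documents, assumed.** Two-sided 5% (no alpha is stated for these p-values); log10 load normal with mean 5 to 7 and SD 1.5 to 2; true correlation 0.2 to 0.6. The plan gives no power, SD or expected association for these tests, so there is no figure of its own to reproduce.

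**Step 1, class sizes.** Low = Φ((4 − mean)/SD); High = 1 − Φ((7 − mean)/SD).

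- Mean 7, SD 1.5: Low = Φ(−2) = 2.3%, or 45 × 0.023 ≈ 1 patient.
- Mean 5.5, SD 2: Low = High = Φ(−0.75) = 22.7%, or 45 × 0.227 ≈ 10 patients.

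Over means 5.5 to 7 and SDs 1.5 to 2, the smallest class holds about 2 to 23% of patients.

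**Step 2, check of the simulation.** The Fisher-z formula for Pearson power is Φ(√(n − 3) × atanh(ρ) − 1.96), with √42 = 6.481.

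- ρ = 0.3: Φ(6.481 × 0.3095 − 1.96) = Φ(0.05) = 0.52
- ρ = 0.4: Φ(6.481 × 0.4236 − 1.96) = Φ(0.79) = 0.78
- ρ = 0.5: Φ(6.481 × 0.5493 − 1.96) = Φ(1.60) = 0.945

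The simulation (2,500 runs per setting, outcome rounded to whole days) gave 0.51–0.53, 0.77–0.80 and 0.94–0.95. At ρ = 0, Spearman and Kruskal-Wallis reject in about 4 to 5% of runs.

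**Step 3, power for a continuous variable such as symptom days** (n = 45, mean 6, SD 1.5):

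| ρ | Spearman, uncut | Three classes, order used | Kruskal-Wallis, as planned | Lost by cutting | Lost by ignoring order | Total |
|---|---|---|---|---|---|---|
| 0.2 | 23% | 20% | 14% | 3 | 6 | 9 |
| 0.3 | 48% | 39% | 28% | 9 | 11 | 20 |
| 0.4 | 75% | 63% | 50% | 12 | 13 | 25 |
| 0.5 | 91% | 82% | 72% | 9 | 10 | 19 |
| 0.6 | 99% | 96% | 91% | 3 | 5 | 8 |

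Over all the assumed distributions at n = 45, the total loss is 9–12 points at ρ = 0.2, 15–20 at 0.3, 20–26 at 0.4, 14–21 at 0.5 and 5–9 at 0.6. With n = 40 (mean 6, SD 1.5) it is 18–25 points for ρ = 0.3 to 0.5 and 12.6 at ρ = 0.6.

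The split between the two causes moves with the distribution. At ρ = 0.4 with mean 5 and SD 2, cutting costs 8.3 of 19.9 points. With mean 7 and SD 1.5 it costs 16.1 of 25.3.

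**Step 4, yes/no outcomes** (rank-sum on the full scale against 3×2 Fisher; mean 5.5 to 6.5, SD 1.5 to 2; event rates and odds ratios assumed):

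| Event rate | Odds ratio per SD | Rank-sum | Fisher |
|---|---|---|---|
| 10% | 2 | 23–25% | 10–13% |
| 10% | 3 | 46–47% | 20–27% |
| 20% | 2.5 | 57–58% | 28–32% |
| 50% | 2.5 | 76–77% | 49–56% |

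The uncut test gains in every row. At a 10% event rate neither test reaches 50% power even at an odds ratio of 3.

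**The case against.** The case for leaving the tables alone has four parts.

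- **The analyses are exploratory.** SAP section 1 calls the analyses descriptive, Protocol 12.1 says mainly so, and relating baseline viral load to symptom days or outcome is not a protocol endpoint. This stands and limits the priority. It does not justify the class p-values: if the tables are only descriptive, those should go; if association is to be tested, the better test is free.
- **Viral load is not cut everywhere.** SAP 8.1 l) plans logistic models for discharge by day 8 and day 15 and a Cox model for time to discharge. Figure 15.4.1 gives baseline viral load one coefficient while dose and FDA class have level contrasts, so discharge by day 8 already appears to be modelled uncut. This also stands, and it shows that the uncut analysis is feasible. SAP 8.1 n) mentions viral load by FDA group, but Table 12.1.35, the apparent shell, has no viral load row.
- **The figures rest on assumptions.** A reader might take 14 to 26 points as a property of this trial, or as the price of cutting alone. The documents support neither: they state no alpha, SD or expected association, and about half the loss comes from tests that ignore order.
- **Rare outcomes stay out of reach.** Patients in multi-organ failure or already on mechanical ventilation are excluded, so death and IMV may be uncommon. A reader might infer that uncut testing makes those rows informative. It improves them, but power may remain low under any test, and a plain logistic model may be unstable or separated.

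**Conclusion.** The point holds as a worthwhile, low-priority improvement. Tables 10.2.10 and 12.1.8 discard both the scale and the ordering of a variable that the SAP already holds in log10. If the true correlation with a continuous variable is 0.3 to 0.5, the planned test gives up about 14 to 26 points of power at n = 45, roughly half from cutting and half from ignoring order; at 0.2 or 0.6 it is about 5 to 13 points, allowing for n = 40. All of this assumes normal log10 load with mean 5 to 7 and SD 1.5 to 2, and a two-sided 5% level.

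The documents do not support a wider claim that the trial's conclusions are compromised. The primary safety objective, the arm-wise efficacy summaries and the stated basis for dose selection do not depend on these tests.

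**What to change.** In SAP 8.1 a) and Tables 10.2.10, 12.1.8 and 12.1.11, test log10 baseline viral load uncut:

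- **Symptom days and hospital days:** Spearman correlation with 95% confidence interval.
- **Yes/no outcomes:** rank-sum test. Add an odds ratio per log10 only where there are enough events; otherwise use an exact or penalised logistic model.
- **Mild, Moderate, Severe:** Jonckheere-Terpstra test.
- **Time to negative detection:** a single log10 term in a Cox model, the method the SAP already uses for time to discharge, because times may be censored.

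Rank undetectable baseline values lowest. Keep the three classes as descriptive columns without p-values, and print their cut points in log10 copies/mL.

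The cost is SAP wording and a few table footnotes, with the same data and software. The one downside is that a correlation or an odds ratio per log10 is slightly less immediate to read than three columns, which is why the columns stay.
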